### 11.3 Risks associated with the IVUS procedure

The IVUS device is designed to function as a conventional, rotating core catheter which has an excellent safety record. Experience with IVUS throughout the world has shown that the catheter safety profile is low with potential adverse events associated with the IVUS in the target lesions at a very low rate (<1%).

Other risks associated with using this device are those associated with percutaneous coronary diagnostic (including angiography and IVUS) and treatment procedures. These risks may include, but are not limited to, the following:

- Abrupt vessel closure
- Access site pain, hematoma or hemorrhage
- Allergic reaction (to contrast, antiplatelet therapy, stent material, or drug and polymer coating)
- Aneurysm, pseudoaneurysm, or arteriovenous fistula (AVF)
- Arrhythmias, including ventricular fibrillation
- Balloon rupture
- Bleeding
- Cardiac tamponade
- Coronary artery occlusion, perforation, rupture, or dissection
- Coronary artery spasm
- Death
- Embolism (air, tissue, device, or thrombus)
- Emergency surgery: peripheral vascular or coronary bypass
- Failure to deliver the stent
- Hemorrhage requiring transfusion
- Hypotension / hypertension
- Incomplete stent apposition
- Infection or fever
- Myocardial infarction (MI)
- Pericarditis
- Peripheral ischemia / peripheral nerve injury
- Radiation exposure
- Renal Failure
- Restenosis of the stented artery
- Shock / pulmonary edema
- Stable or Unstable angina
- Stent deformation, collapse, or fracture
- Stent migration or embolization
- Stent misplacement
- Stroke / transient ischemic attack

### 11.4 Measures to Mitigate Risk to Trial Subjects

The following measures will be implemented to minimize risk to the trial subjects:

- Treating physicians will have considerable experience with both the Rotational atherectomy device, ROTA PRO, and the wolverine device.
- Treating physicians will have considerable experience with IVUS imaging techniques
- Study sites will have significant experience with severely calcified lesion percutaneous coronary intervention

Page | 24

**CONFIDENTIAL AND PROPRIETARY:** This document and the information contained there-in may not be reproduced, used or disclosed without written permission from the Principal Investigators.

Version: 11\_dtd02Mar2023

IDE G210030

Effective Date: 3/23/2023

End Date: 2/14/2024

- Serial IVUS measurements will be performed throughout the procedure as specified above
- Final blinded IVUS runs will be read by an experienced interventional cardiologist before the subject is removed from the catheterization laboratory
- Subjects will be rigorously followed over the course of the trial

## 11.5 Anticipated Benefits

The potential benefit of severely calcified lesion preparation with the combination of rotational atherectomy with the RotaPro followed by a cutting balloon with the Wolverine, is to maximize the final minimal stent area as assessed by IVUS, that would translate in a clinical benefit at follow-up. Indeed, there is ample data supporting that larger stented areas at the end of an angioplasty are associated with lower rates of major adverse event or target vessel failure at long term follow-up. (10, 11, 12)

## 11.6 Alternative Therapies

Presently, therapeutic alternatives for patients meeting the ROTACUT inclusion criteria who are scheduled for PCI rotational atherectomy include the following:

- PCI with rotational atherectomy alone or followed by POBA

## 11.7 Justification of Trial

The treatment of severely calcified lesions continues to have high rates of major adverse cardiovascular events. (1-3) Based upon the literature review presented in the Report of Prior Investigation, the utility of cutting balloon device(s) following successful rotational atherectomy has demonstrated larger post stent implantation MSA as compared to rotational atherectomy and plain balloon.(13-16) This trial is designed to prospectively, and in a randomized fashion, evaluate this treatment strategy. Although there are risks to the subjects for participation in the trial, they are anticipated to be similar to the risks of undergoing PCI for severely calcified lesion outside of the trial. The trial endpoints are clinically relevant for the patient population targeted, those with severely calcified lesions. There are no foreseen differences with regard to sex at birth, age at the time of enrollment with respect to this trial endpoints. Therefore, the trial is justified.

## 11.8 Stopping Rules

A stopping rule based on the occurrence of clinically relevant coronary dissection was defined on the basis of literature review. In previous pilot studies evaluating a strategy of rotational atherectomy with or without cutting balloon, the meta-analytic incidence of coronary dissection was 18% (2-sided 95% upper confidence limit = 28%).(13, 14) Therefore, a stopping rule is set at the occurrence of 11 (18% of 60 patients) flow-limiting coronary dissections leading to a periprocedural myocardial infarction.(17) That is, if during

Page | 25

**CONFIDENTIAL AND PROPRIETARY:** This document and the information contained there-in may not be reproduced, used or disclosed without written permission from the Principal Investigators.

Version: 11\_dtd02Mar2023

IDE G210030

Effective Date: 3/23/2023

End Date: 2/14/2024

the enrollment phase, 11 episodes of flow-limiting coronary dissection associated with periprocedural myocardial infarction occur, patient recruitment will be terminated.

If the trial is terminated prematurely or suspended, the sponsor shall promptly inform the clinical investigators and regulatory authorities of the termination or suspension and the reason(s) for this. The investigator shall then promptly inform the reviewing IRB. The sponsor will, as soon as possible, provide a written statement to the investigators to enable prompt notification of the IRBs. If the trial is terminated early, follow-up visits will continue for all enrolled subjects for the intended length of the study.

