### 6.4.2 SECONDARY ENDPOINTS

- IVUS endpoints will be assessed at the following time points
  - Final IVUS (post Stent and post-dilatation)
    - In-segment Minimum lumen area ( $\text{mm}^2$ ), as assessed by IVUS after stent implantation and (optional) post-dilatation, referenced to the EEM
    - Minimum stent expansion (as defined as MSA  $\text{mm}^2$ ), as assessed by IVUS directly after stent implantation and post-dilatation
    - Mean stent expansion (%) –defined as mean stent area divided by the mean reference lumen area, where reference lumen area will be the average of the proximal and distal 10mm to the stent and/or the reference EEM at the site of MSA
    - Any dissection
    - Any malapposition
  - Pre-stent implantation post RA and CBA or POBA
    - Any dissection
    - Assessment of calcium fracture
- Angiographic endpoints measured in both in-stent, injured and in-segment (defined as injured or stent (whichever is larger) plus 5mm either end as feasible)

Page | 13

---

**CONFIDENTIAL AND PROPRIETARY:** This document and the information contained there-in may not be reproduced, used or disclosed without written permission from the Principal Investigators.

Version: 11\_dtd02Mar2023

IDE G210030

---

- Acute lumen gain (mm)
- Final residual diameter stenosis (%)
- Pre, pre-stent, and final minimum lumen diameter (mm)
- Pre-stent and final dissection type B or greater
- Final perforation (Ellis type  $\geq 2$ )
- Final side branch closure ( $\geq 1.5$ mm)
- Device-related endpoints as defined by any problems related to the devices, including but not limited to: balloon rupture, blade detachments, difficulty in withdrawing/advancing the device, or other device related problems as identified by the investigator.
- Clinical endpoints at 30-day and 270 day follow-up:
  - All-cause death (and further classified as cardiac and non-cardiac)
  - Myocardial infarction (as defined by the SCAI definition and Universal definitions, including peri-procedural myocardial infarction)
  - Target lesion revascularization
  - Target vessel revascularization
  - Stent thrombosis (definite/probable)
  - Major bleeding (BARC 3 or 5)
  - Vascular complications
  - Target Lesion Revascularization
  - Functional status (according to CCS class)

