### 13.3 Clinical Events Committee

The ROTACUT Clinical Events Committee (CEC) is an independent adjudicating committee which conducts ongoing review of all potential endpoints. The CEC consists of physicians with specialty in cardiology and/or interventional cardiology, who are impartial, independent of the investigator(s) and who have no financial, scientific, or other conflict of interest with the trial. The activities of the CEC along with the definitions and detailed process are described in the CEC Charter.

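### The stopping count of 11 is taken from an 18% rate for coronary dissection in general, but the rule counts only flow-limiting dissection leading to periprocedural MI

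*Combined protocol and SAP*

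**What the plan says.** Section 11.8 (Stopping Rules) builds the rule in three steps.

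- It opens with the subject of the rule: "A stopping rule based on the occurrence of clinically relevant coronary dissection was defined on the basis of literature review".
- It then gives the literature figure, attributed to references 13 and 14: "the meta-analytic incidence of coronary dissection was 18% (2-sided 95% upper confidence limit = 28" per cent. No severity or MI qualifier is attached to this figure.
- It then draws the rule as a consequence: "a stopping rule is set at the occurrence of 11 (18% of 60 patients) flow-limiting coronary dissections leading to a periprocedural myocardial infarction". Reference 17 is cited for this event. Recruitment ends if 11 such episodes occur during enrolment.

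Elsewhere the protocol grades dissection. Section 6.4.2 lists dissection of any degree on IVUS and, separately, an angiographic endpoint, "Pre-stent and final dissection type B or greater". Neither is the event that the stopping rule counts. For MI, section 6.4.2 uses an endpoint "as defined by the SCAI definition and Universal definitions, including peri-procedural myocardial infarction". Section 13.3 adds that "The activities of the CEC along with the definitions and detailed process are described in the CEC Charter"; the Charter was not among the documents supplied.

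**The concern.** The same percentage is applied to two different events in consecutive sentences. The rate is for coronary dissection. The count needs a dissection that limits flow and also leads to a periprocedural MI. As worded, every counted event is a dissection, but not every dissection is counted. Carrying 18% over unchanged is valid only if all the dissections behind the rate met both added conditions. The documents do not say that they did, and they give no incidence for the narrower event.

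This is the only numerical stopping rule in the documents. If the counted event is much rarer than 18%, the threshold lies far above what would be expected, and recruitment could continue through a marked excess of a serious complication without the rule operating. An IRB or regulator reading section 11.8 cannot tell what rate of the counted event the rule protects against, or how likely it is to trigger.

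**Working it through.** **Inputs**

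- Reference incidence of coronary dissection: 18%, upper limit 28% (section 11.8).
- Stopping count: 11, described as 18% of 60 (section 11.8).
- Total sample: 60, both arms pooled (section 9.2).
- Share *f* of dissections that are flow-limiting and lead to periprocedural MI: not in the documents. It is an assumption here, varied from 100% to 10%.
- At most one counted event per patient: also an assumption.

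**The plan's own figure.** 0.18 × 60 = 10.8, rounded to 11, and 11/60 = 18.3%. The figure reproduces, as a count of all dissections.

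**Chance of reaching the count.** With X ~ Binomial(60, p) and p = *f* × 0.18 or *f* × 0.28, the expected number of counted events is 60p and the chance of stopping is P(X ≥ 11).

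| Share qualifying (assumed) | p at 18% | Expected | P(X ≥ 11) | p at 28% | Expected | P(X ≥ 11) |
|---|---|---|---|---|---|---|
| 100% | 0.180 | 10.8 | 0.53 | 0.280 | 16.8 | 0.97 |
| 75% | 0.135 | 8.1 | 0.18 | 0.210 | 12.6 | 0.74 |
| 50% | 0.090 | 5.4 | 0.017 | 0.140 | 8.4 | 0.21 |
| 25% | 0.045 | 2.7 | 0.00007 | 0.070 | 4.2 | 0.003 |
| 10% | 0.018 | 1.1 | 1 × 10⁻⁸ | 0.028 | 1.7 | 8 × 10⁻⁷ |

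**Working back from the count**

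- P(X ≥ 11) = 0.50 needs p = 0.177. As a share of dissections this is 0.1768/0.18 = 98% at the reference rate, or 0.1768/0.28 = 63% at the upper limit.
- P(X ≥ 11) = 0.10 needs p = 0.120. This is 0.1201/0.18 = 67% at the reference rate, or 0.1201/0.28 = 43% at the upper limit.

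**What the rule would miss.** Suppose half of dissections qualify, so that the background rate of the counted event is 9%. If that rate doubled to 18%, the rule would still have only about an even chance (0.53) of triggering.

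No replacement count can be calculated, because the documents give no incidence for the event being counted.

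**The case against.** **The cited studies may already use a restricted event.** The section opens by speaking of clinically relevant dissection, so the 18% could be shorthand for that. References 13 and 14 were not available, so this cannot be excluded. It limits the finding to the wording: the threshold has not been shown to be wrong, only unsupported as written. But the qualifier describes the subject of the rule and is not attached to the 18%, and clinically relevant is not the same as flow-limiting with MI.

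**A low chance of stopping at the background rate is no defect.** This is right. A safety rule should seldom trigger when events occur as expected, and a 53% chance of stopping at the reference rate would be a poor rule too. The table illustrates how strongly the rule depends on an unstated share; it does not measure harm in this trial. It does not rescue a count borrowed from a broader event.

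**A threshold need not equal a background incidence.** The sponsor and regulator may set a tolerability limit on other grounds. They may, but section 11.8 gives no other ground and presents the count as following from the 18%.

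**The section has had regulatory attention, and other safeguards exist.** The revision history records clarifications of section 11.8 in response to FDA in versions 9.0 and 9.2. There is also unblinded review of the final IVUS (sections 7.3.3 and 11.4), 48-hour reporting of serious adverse events (12.3), a Medical Monitor (12.5) and a Clinical Events Committee (12.6). These reduce the practical harm. None of them sets a count or supplies the missing rate.

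**The MI definition is a side issue.** Agreed. It may be settled in the Charter, and the finding does not depend on it.

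**Conclusion.** The concern holds. As worded, the count of 11 rests on the incidence of one event and is applied to a narrower one, for which no incidence is given. At the 18% reference rate the chance of stopping falls from 0.53 if every dissection qualifies to 0.017 if half do and 0.00007 if a quarter do. At the 28% upper limit the corresponding figures are 0.97, 0.21 and 0.003. These rest on an exact binomial for 60 patients, at most one event per patient, and an assumed qualifying share.

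Confidence is high that the text does not connect the rate to the counted event. Whether the cited studies would connect them is unknown. This must be corrected because it concerns the trial's only numerical stopping threshold; it does not touch the primary MSA analysis.

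**What to change.** Amend section 11.8 as follows.

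1. Make the reference incidence and the counted event the same event. If the 18% from references 13 and 14 already refers to flow-limiting dissection with periprocedural MI, say so.
2. Otherwise, re-derive the count from an incidence for the counted event, or state the separate reasoning that justifies 11.
3. State the chance of stopping at the reference rate and at its upper limit.
4. In the same edit, say which MI definition governs the rule: reference 17, cited in section 11.8, or the SCAI and Universal definitions in section 6.4.2. Also reconcile the two descriptions of the link between dissection and MI in section 11.8, one causal and the other only an association.

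The event, the tolerable rate and the threshold are for the sponsor, the medical monitor and the regulator to set.

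The cost is a short amendment, with no extra patients or procedures. The drawback is that a rule able to trigger carries some chance of a false stop, which the amended section should state.

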## 6 INVESTIGATIONAL PLAN

### 6.1 Study Design

This is a prospective, multi-center randomized pilot study of 60 patients with stable CAD undergoing PCI for a *de novo* calcified lesion with drug eluting stent implantation. Patients with target vessel reference diameter of  $\geq 2.5$  mm and  $\leq 4.0$  mm, lesion length  $\geq 5$  mm and moderate to severe calcification confirmed by angiography will undergo pre-procedural IVUS assessment, if feasible. Subjects with moderate or severe calcification for at least 5 consecutive mm in a *de novo* lesion, confirmed by angiography, will be enrolled. Enrolled subjects will be randomized in a 1:1 fashion to either ROTA + CUT or ROTA + POBA group. Rotational Atherectomy will be performed using Burr: Artery ratio of 0.4 to 0.6 in both arms. Intra-procedural IVUS pullbacks will be performed after lesion preparation, prior to stent implantation and after stenting. Upon PCI completion, operators will be blinded to final, post angioplasty IVUS results. An unblinded physician will review the results of this final IVUS run for safety signals not present on fluoroscopy. All patients will receive a drug-eluting stent after plaque preparation.

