### 7.3.3 Intravascular Ultrasound Assessment

Intravascular ultrasound assessment for off-line analysis will be performed with the following strategy. The 60Mhz OptiCross™ IVUS catheter (Boston Scientific, Marlborough, MA, USA) using automated pull-back at 1mm/s. The catheter will be advanced at least 5 mm distal to the target lesion.

- 1) at baseline, prior to any intervention, if possible. This IVUS run is optional
- 2) after lesion preparation defined as RA + POBA or RA + CBA, and
- 3) at the end of the procedure. This will be following completion of the interventional procedures per the interventional cardiology investigator.

During the procedure, any additional IVUS runs and assessments deemed clinically indicated by the treating physician to guide the procedure will not be precluded from being performed; these will occur prior to the Final post-angioplasty IVUS run.

Only after the operator deems the procedure to be finished, will the final post angioplasty IVUS run be performed for endpoint assessment. In order to reduce bias, operators will be blinded to the final IVUS run pullback images and no additional stent placement or post dilation is allowed after the Final IVUS run. Blinding will be performed by either turning the IVUS console results away from the primary investigator in the room, or having the primary investigator turn away, if the former is not feasible.

To ensure safety, an unblinded physician will be available at the end of the procedure to review the results of the Final IVUS run for safety signals not present on fluoroscopy. If the unblinded physician has any safety-related concerns, the operator will take immediate actions to ensure the safety of the patient.

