## 12.2 Causality Relationship

Relatedness of the AE to the index procedure or the study device itself will be initially judged by the investigator. For events eligible for CEC adjudication, the CEC will ultimately adjudicate procedure and device-relationship.

Each AE will be classified according to the following levels of causality:

- 1) **Not related:** relationship to the device or procedures can be excluded when:
  - the event is not a known side effect of the product category the device belongs to or of similar devices and procedures;
  - the event has no temporal relationship with the use of the investigational device or the procedures;
  - the serious event does not follow a known response pattern to the medical device (if the response pattern is previously known) and is biologically implausible;
  - the discontinuation of medical device application or the reduction of the level of activation/exposure - when clinically feasible – and reintroduction of its use (or increase of the level of activation/exposure), do not impact on the serious event;
  - the event involves a body-site or an organ not expected to be affected by the device or procedure;
  - the serious event can be attributed to another cause (e.g. an underlying or concurrent illness/ clinical condition, an effect of another device, drug, treatment or other risk factors);
  - harms to the subject are not clearly due to use error;

Page | 28

**CONFIDENTIAL AND PROPRIETARY:** This document and the information contained there-in may not be reproduced, used or disclosed without written permission from the Principal Investigators.

Version: 11\_dtd02Mar2023

IDE G210030

---

- In order to establish the non-relatedness, not all the criteria listed above might be met at the same time, depending on the type of device/procedures and the serious event.

2) **Unlikely:** the relationship with the use of the device seems not relevant and/or the event can be reasonably explained by another cause, but additional information may be obtained.

3) **Possible:** the relationship with the use of the investigational device is weak but cannot be ruled out completely. Alternative causes are also possible (e.g. an underlying or concurrent illness/ clinical condition or/and an effect of another device, drug or treatment). Cases where relatedness cannot be assessed or no information has been obtained should also be classified as possible.

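### The stopping count of 11 in section 11.8 is pooled over both arms and, if control events are rare, reacts weakly to excess harm in the cutting-balloon arm; adding a count of 6 in that arm is a cheap, partial improvement.

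*Combined protocol and SAP*

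**What the plan says.** Section 11.8 takes its benchmark from the literature. It introduces the sources with the words "In previous pilot studies evaluating a strategy of rotational atherectomy with or without cutting balloon". Their combined rate of dissection is put at 18%, and the upper 95% limit at 28%. From the 18% it concludes that "a stopping rule is set at the occurrence of 11 (18% of 60 patients) flow-limiting coronary dissections leading to a periprocedural myocardial infarction". The operative sentence is that if, during enrollment, "11 episodes of flow-limiting coronary dissection associated with periprocedural myocardial infarction occur, patient recruitment will be terminated". Neither sentence names an arm, and the 11 is expressed as a share of all 60 patients.

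Section 6.1 sets the allocation: "Enrolled subjects will be randomized in a 1:1 fashion to either ROTA + CUT or ROTA + POBA group". That gives about 30 patients per arm.

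The other safety provisions are these:
- A same-session reading of the final IVUS run (7.3.3 and 11.4): "an unblinded physician will be available at the end of the procedure to review the results of the Final IVUS run".
- Evaluation of unanticipated adverse device effects (12.1).
- Adjudication of relatedness (12.2), where "the CEC will ultimately adjudicate procedure and device-relationship"; under 12.6 the committee is blinded to arm.
- Reporting of serious adverse events within 48 hours (12.3).
- Medical Monitor review of all adverse events (12.5).

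None of them states a number by arm.

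**The concern.** The trial compares cutting-balloon with plain-balloon preparation after rotational atherectomy. If the cutting balloon causes flow-limiting dissections with infarction, the excess falls in one arm only. A pooled count adds that arm's events to those of an arm without the excess, yet its threshold is scaled to both arms together. The rule is therefore least responsive when excess harm sits in the experimental arm and control events are rare. What is at stake is how many further patients are randomized to ROTA + CUT before the plan's numerical rule acts.

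**Working it through.** **Inputs.** Total 60 (9.2), 1:1 allocation (6.1), benchmark 18% with upper limit 28% and stopping count 11 (11.8). Exactly 30 per arm is assumed. The documents give no rate for the counted event in either arm, so every event rate below is an assumption and a range is shown.

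**The plan's figure.** 0.18 × 60 = 10.8, rounded up to 11. This reproduces the stated count (11/60 = 18.3%).

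**What 11 means for one arm.** With no control events, stopping needs 11 of 30 in ROTA + CUT, or 36.7%. That is about twice the 18% benchmark and above its 28% upper limit. Ten of 30 is 33% (exact 95% CI 17% to 53%) and does not stop recruitment.

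**The same derivation for one arm.** 0.18 × 30 = 5.4, rounded up to 6.

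**Chance of stopping by patient 60.** Let C ~ Binomial(30, control rate) and E ~ Binomial(30, ROTA + CUT rate), independent. The present rule stops with probability P(C + E ≥ 11). With the addition it stops with probability P(C + E ≥ 11 or E ≥ 6), summed exactly over the joint distribution.

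| Control rate | ROTA + CUT rate | Present rule | With 6 added |
|---|---|---|---|
| 2% | 10% | 0.0006 | 0.073 |
| 2% | 15% | 0.009 | 0.29 |
| 2% | 18% | 0.029 | 0.46 |
| 2% | 28% | 0.27 | 0.88 |
| 10% | 28% | 0.61 | 0.89 |
| 18% | 28% | 0.85 | 0.93 |

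**Sensitivity to arm size.** If ROTA + CUT has 26 or 34 of the 60 patients, the figures at 2% and 20% are 0.024 to 0.42 and 0.10 to 0.70. With 30 they are 0.053 to 0.57.

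**ROTA + CUT events averted.** This comes from simulation with 30 patients per arm in random order, control rate 2%, and each event known before the next patient is enrolled. Mean ROTA + CUT events when recruitment ends, present rule then with the addition:
- 10%: 3.00 and 2.97, about 0.04 averted before rounding
- 15%: 4.49 and 4.23, about 0.3
- 18%: 5.39 and 4.83, about 0.6
- 28%: 8.09 and 5.81, about 2.3 (mean enrollment falls from 57.6 to about 41)

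**Price when the arms do not differ.** Chance of stopping, present rule then with the addition:
- 5% in both arms: 0.0002, 0.0034
- 10%: 0.034, 0.088
- 15%: 0.28, 0.39
- 18%: 0.53, 0.62

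**How much is due to pooling.** The equal-rate figures also show that the present rule is insensitive when both arms are harmed: at 10% in each arm it stops with probability 0.034. Pooling cannot explain that. The cause is that 18% is a rate for any coronary dissection, whereas the count is restricted to flow-limiting dissections with periprocedural infarction.

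**The case against.** The strongest reply is that the addition treats the lesser cause. The 6 carries over the same 18% any-dissection benchmark, so it inherits the mismatch: a fivefold excess of 10% over 2% is still missed about 93% of the time. The largest gains need the narrow event to be as frequent in ROTA + CUT as any dissection was in the source studies, or more so. The rule only ends recruitment, so a late trigger spares few patients, and any delay in learning of events reduces the saving further. The added count is also not comparative: 6 events against 4 stops the trial as readily as 6 against 0. All of this stands, and it limits the size of the benefit.

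It is also fair to say that the pooled count matches its source, since the 18% comes from strategies with and without a cutting balloon, and that the revision history records two clarifications of the rule in response to FDA. That explains the form of the rule. It does not make the rule sensitive to harm in one arm.

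A reader might infer that harm from the cutting balloon could go unnoticed until the 11th event. The documents do not support that. Operators know the treatment, serious events are reported within 48 hours, the Medical Monitor sees all adverse events, and unanticipated device effects, including an unexpected degree of incidence, must be evaluated. On the final scans, "Final blinded IVUS runs will be read by an experienced interventional cardiologist before the subject is removed from the catheterization laboratory". These provisions act event by event or by judgment, however, and the blinded events committee cannot count by arm. They soften the gap without supplying a threshold.

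A reader might also infer that the cutting balloon is the only exposure that differs between arms, so that control events must be rare. Sections 4.1 and 6.1 give the control arm plain balloon angioplasty, and no section states the control rate of the counted event. If control events are common, the gain is small.

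**Conclusion.** The concern holds in a limited form. The count is pooled, no section gives a threshold by arm, and if control events are rare the rule responds weakly to excess harm in ROTA + CUT. At an assumed 2% control rate, adding 6 raises the chance of stopping substantially for ROTA + CUT rates of 15% to 28%, very little at 10%, and the mean number of ROTA + CUT events averted is modest except near 28%. These sizes rest on assumed rates, about 30 patients per arm and immediate knowledge of events.

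The documents do not support reading pooling as the main weakness of section 11.8, or the addition as a full repair. The benchmark mismatch is the larger problem and remains. Nor do they support a lower count such as 3: that needs an agreed rate for the counted event, which they do not give. With 3, the chance of stopping at 5% in both arms would be 0.19.

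**What to change.** In 11.8, keep the pooled 11 and add: *Recruitment will also be terminated if 6 such events occur in the ROTA + CUT arm.* State the derivation beside it (18% of 30 = 5.4, rounded up).

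In 12.5, add: *The Medical Monitor receives the tally of these events by arm.* The events committee stays blinded. The text should also say whether site-reported or adjudicated events count toward the tally.

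The cost is two sentences and a short procedure, since the Medical Monitor's present duties do not include arm tallies. No extra patients are needed. Section 6.5 places randomization in the EDC, so a tally by arm should be obtainable there, but the documents do not confirm it. The statistical price is the added stopping at equal rates shown above: negligible at 5%, about 5 percentage points at 10% and about 11 at 15%.

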### 9.2 Sample Size Rationale

The current study is investigating a novel approach for lesion preparation before stent implantation. As there is limited data available to estimate the expected MSA after rotational atherectomy + cutting balloon atherectomy strategy, no formal sample size calculation was performed. A sample size of 60 patients (total n=60) was chosen for this study. However, a sample size of 60 patients will be powered to detect effect sizes as listed below, given an estimated MSA of  $5.50\text{mm}^2 \pm 2.36\text{mm}^2$ , an equal variance, and a two-sided alpha of 0.05.

Table: Power Calculation

Sample Size	Effect Size (mean difference in MSA)	Power
60	1.6	0.733
60	1.7	0.783
60	1.8	0.828
60	1.9	0.866

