## 12.5 Medical Monitor

A Medical Monitor will be available to sites on a 24/7 basis for the duration of the trial to address protocol related medical questions from participating sites and will review all AEs to identify events that require formal reporting measures.

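### The safety stop in 11.8 is one fixed count of 11 at every stage of enrollment; lower counts by number treated would protect early patients better at small cost

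*Combined protocol and SAP*

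**What the plan says.** Section 11.8 starts from a pooled literature incidence of coronary dissection of 18%, with an upper 95% confidence limit of 28%. From this it concludes that "a stopping rule is set at the occurrence of 11 (18% of 60 patients) flow-limiting coronary dissections leading to a periprocedural myocardial infarction". The operating sentence adds that if, during enrollment, "11 episodes of flow-limiting coronary dissection associated with periprocedural myocardial infarction occur, patient recruitment will be terminated". It names no number treated, no interim look and no smaller early count.

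The denominator comes from section 9.2: "A sample size of 60 patients (total n=60) was chosen for this study". That section also describes the lesion-preparation approach as novel.

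Other safety oversight exists, without a numerical trigger. Under section 12.5 the Medical Monitor "will review all AEs to identify events that require formal reporting measures". Sections 12.6 and 13.3 give the Clinical Events Committee an adjudication role. Section 11.8 also covers premature termination or suspension in general terms.

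**The concern.** A count of 11 matches its stated 18% basis only once all 60 patients have been treated, when there is no recruitment left to end. At any earlier point the same count stands for a higher observed rate, and the earlier the point, the higher that rate. An early cluster, when experience with the combined strategy in this trial is smallest, can reach 10 events and leave the only prespecified stop untouched. The plan also does not report how the rule behaves: neither the chance of stopping nor the expected number treated is given for any event rate.

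**Working it through.** **Inputs.** Count 11, reference incidence 18% and upper limit 28% (section 11.8); 60 patients in total (sections 6.1 and 9.2). True rates of 5%, 10%, 40% and 50% are assumptions; the documents give no rate for the event counted.

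**The plan's figure.** 0.18 × 60 = 10.8, rounded up to 11. It reproduces; 11/60 = 18.3%.

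**What 11 events means earlier.** The observed rate at the trigger is 11/n.

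| Patients treated (n) | 11/n |
|---|---|
| 15 | 73.3% |
| 20 | 55.0% |
| 30 | 36.7% |
| 40 | 27.5% |
| 60 | 18.3% |

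Ten events, one short of the trigger, would be 100% of 10 patients, 66.7% of 15 and 50% of 20.

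**Fixed rule.** With at most one event per patient and a common true rate p, the chance of having stopped by patient n is P(Bin(n, p) ≥ 11).

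| True rate | By 20 | By 30 | By 60 |
|---|---|---|---|
| 18% | 0.0002 | 0.012 | 0.526 |
| 28% | 0.010 | 0.194 | 0.970 |
| 40% (assumed) | 0.128 | 0.709 | >0.999 |

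**Illustrative added boundary.** From patient 5 on, stop when the running count reaches the smallest r with P(Bin(n, 0.18) ≥ r) ≤ 0.03, and never require more than 11. For example, P(Bin(10, 0.18) ≥ 5) = 0.021 and P(Bin(20, 0.18) ≥ 8) = 0.018. The counts are 4 of 5, 5 of 10, 7 of 15, 8 of 20 and 9 of 25. From patient 30 the cap of 11 applies, so the rule is then the existing one.

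Operating characteristics come from following the event count patient by patient. Let s(n) be the probability of first reaching the boundary at patient n. Then P(stop) = Σ s(n), and expected number treated = Σ n·s(n) + 60·(1 − P(stop)).

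| True rate | Expected treated: fixed → added | Stop by patient 30: fixed → added | Stop by patient 60: fixed → added |
|---|---|---|---|
| 5% (assumed) | 59.999 → 59.986 | both below 0.1% | 0.02% → 0.04% |
| 10% (assumed) | 59.77 → 59.55 | 0.01% → 0.5% | 3.4% → 3.7% |
| 18% | 54.0 → 52.1 | 1.2% → 6.8% | 52.6% → 53.1% |
| 28% | 39.1 → 32.9 | 19.4% → 38.1% | 97.0% → 97.0% |
| 40% (assumed) | 27.5 → 17.0 | 70.9% → 83.8% | both >99.9% |
| 50% (assumed) | 22.0 → 10.6 | 95.1% → 97.9% | both >99.9% |

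At a true 18%, the chance of stopping by patient 20 rises from 0.02% to 5.3%.

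**The case against.** **The 28% comparison.** A reader might note that 11/39 = 28.2% and 11/40 = 27.5%, and infer that the rule is defective because before patient 40 it cannot act at or below the plan's own upper limit. The arithmetic is right, but the inference is not supported. Section 11.8 gives 28% as a confidence limit on a literature incidence and does not use it as a stopping threshold. Any boundary that allows for small-sample noise must also sit above such a figure early on: the illustration needs 50% at 10 patients and 40% at 20, and it returns to 11 from patient 30.

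**Different event.** The 18% and 28% describe coronary dissection, whereas the count covers flow-limiting dissection with periprocedural infarction. This stands. If the counted event occurs in 5% to 10% of patients, a boundary built on 18% adds almost nothing. It is a reason to choose the reference rate carefully; it does not justify leaving the count fixed.

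**Early protection exists.** It would be too strong to say that the first half of enrollment is essentially unprotected. At an assumed 40% the fixed rule has stopped by patient 30 with probability 71%, and at 50% with probability 95%.

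**Other safeguards.** Serious events are reported within 48 hours (12.3), the Medical Monitor reviews all adverse events (12.5), and an unblinded physician reads each final IVUS run (7.3.3). The unanticipated-effect definition covers degree of incidence (12.1), and termination or suspension outside the count is not ruled out (11.8). An early cluster would therefore not go unexamined. But none of these carries a number, so none does the work of a prespecified boundary.

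**Small pilot.** This is a 60-patient study of commercially available devices (4.2), and a simple count is easy to run. That limits how much the point weighs; it does not remove it.

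**Conclusion.** The point holds as a cheap improvement to a stated safety rule. Section 11.8 has no boundary by number treated and no stated operating characteristics, so up to 10 counted events in the first 10, 15 or 20 patients leave its only numerical stop untriggered. A boundary for the first half of enrollment would cut expected patients treated by about 6 at a true 28% (39.1 to 32.9) and by about 10 at an assumed 40% (27.5 to 17.0). The price at a true 18% is 5.6 percentage points more chance of stopping by patient 30 (6.8 − 1.2) and 0.5 points more over the whole trial.

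These sizes assume at most one event per patient (the rule counts episodes), independent patients, a common rate with both arms pooled, and each outcome known before the next patient is treated. They also treat the event counted as occurring at the stated rates, which the documents do not establish. The documents do not support the inference that the rule breaches a 28% limit the plan set for itself, nor that patients have no other safety oversight.

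**What to change.** In section 11.8, keep 11 as the overall cap and add a short table of lower stopping counts by number treated for roughly the first 30 patients. An exact binomial boundary checked after each patient is one way to build it. Base it on a reference rate that the sponsor justifies for flow-limiting dissection with periprocedural infarction, rather than carrying over the 18% for any dissection. State the chance of stopping (by mid-enrollment and overall) and the expected number treated at that rate and at one or more higher rates. Say who keeps the running tally. The acceptable rates and the counts themselves are for the sponsor and medical monitor to decide.

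The cost is one table and a tally fed by the existing 48-hour reporting, with no extra patients. The statistical cost is a higher chance of an early stop when the true rate equals the reference. It should be disclosed with the table, and it can be reduced by a stricter P-value cut-off or a later first look.
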